4.3.5. Ophthalmic Variables

Ophthalmic Examination. The following ophthalmic examination variables will be analysed by shift table from Baseline to the pre-injection examination on Month 24 or last visit available whichever comes later (normal/abnormal, unless otherwise specified below):

- Examination of the motility
- Inspection of the lids/lacrimal/lashes
- Examination of the conjunctiva/sclera
- Inspection of the cornea
- Examination of the iris
- Examination of the pupils
- Inspection of the lens status (aphakic, pseudo-phakic, phakic; if phakic, nuclear/PSC/cortical 0, 1, 2, 3, 4), including a listing of subjects with a change in lens status for study eye and (separately) for fellow eye
- Examination of the posterior vitreous detachment
- Inspection of the optic nerve
- Inspection of the macula
- Examination of the retinal vessels

The following ophthalmic examination variables will be analysed by shift table from Baseline through Month 24 or last visit available whichever comes later, on a monthly basis (normal/abnormal, unless otherwise specified below), and from pre-injection to post-injection at each monthly injection

- Examination of the anterior chamber activity: Cells (0, trace, 1+, 2+, 3+, 4+)
- Inspection of the vitreous haze (0, 1+, 2+, 3+, 4+)
- Examination of the vitreous haemorrhage

- Examination of peripheral retina

Intraocular Pressure. IOP will be summarized by visit, including all pre-injection, “IOP after first injection”, and “IOP after second injection” measurements for applicable visits. An additional tabular summary of the percentage of subjects in categories of IOP will be presented by treatment group, visit, and injection time (pre-injection, IOP after first injection, IOP after second injection).

“IOP after injection” is defined as the IOP measurement that is closest in time to the protocol-specified post-injection timepoint (but at least 30 minutes post-injection). If there are two closest measurements equidistant to this timepoint, then the measurement after the protocol-specified timepoint will be used.

Mean IOP over time of all scheduled measurements (pre-injection, IOP after first injection, and IOP after second injection) will be plotted.

4.3.6. Clinical Laboratory

All laboratory data will be listed and values falling outside normal ranges will be identified, whether they will be deemed clinically relevant or not.

Laboratory data will also be summarized in tables presenting values at each scheduled visit up through the Month 24 visit.

Value changes from Baseline to each scheduled visit up through the Month 24 visit.

A summary table of all analytes with the Baseline mean and the mean change from Baseline to the last value observed.

A summary table of all analytes with the Baseline median and the median change from Baseline to the last value observed.

The following parameters will be summarized:

- Hematological parameters (hemoglobin, white blood cells, platelets, neutrophils (absolute numbers), lymphocytes (absolute numbers), monocytes (absolute numbers), eosinophils (absolute numbers), basophils (absolute numbers)),
- Renal function parameters (serum creatinine and BUN),
- Hepatic function parameters (serum bilirubin, alkaline phosphatase, GGT, SGOT/AST, and SGPT/ALT),
- Electrolytes (sodium, potassium, chloride, carbon dioxide, calcium, and phosphate),
- Complete urinalysis parameters (complete urinalysis including specific gravity, protein, blood, etc.),
- Serum pregnancy test (if of child-bearing potential).

Additional urine or serum pregnancy testing may be performed during the study at the discretion of the investigator, or in accordance with local requirements or regulations.

The incidence of subjects with “Notable Laboratory Values” after the first dose of study drug will be evaluated using the criteria for Notable Laboratory Values given below. Only data

collected after the first dose of study drug, up to the laboratory data taken at the Month 18 visit or 30 days after last dose will be included.

Subject listings of all notable laboratory values will also be provided; for each subject who has an analyte with a notable value, all values of that analyte taken during the study will be presented in the listing, and the notable value, and any values outside of normal limits, will be identified.

For this “Notable Laboratory Values” analysis, *all* laboratory values after randomization will be taken in account, i.e., any values obtained after Day 1, at unscheduled visits, as well as values from the regularly scheduled laboratory visit at Month 18. Three Notable Laboratory Values tables and accompanying subject listings will be presented: (1) notable abnormalities for subjects with normal Baseline results, (2) notable abnormalities for subjects with abnormal Baseline results and (3) notable abnormalities without regard to Baseline abnormalities (i.e., normal, or abnormal Baseline results). The table without regard to Baseline abnormalities will be a composite of the previous two tables (normal Baseline, abnormal Baseline).

Lab analytes and primary criteria used for Notable Laboratory Values:

- a. HEMATOLOGY
 - i. Hemoglobin $< 0.75 \times$ Baseline
 - ii. Platelets < 75 or > 750 ($10^9/L$)
 - iii. WBC count < 2.5 or > 17.5 ($10^9/L$)
 - iv. Neutrophils (absolute) $< 0.5 \times LLN$ or $> 1.5 \times ULN$
 - v. Eosinophils (absolute) $> 1.5 \times ULN$
 - vi. Lymphocytes (absolute) $< 0.5 \times LLN$ or $> 1.5 \times ULN$
- b. LIVER FUNCTION
 - i. Total bilirubin $> 1.5 \times ULN$
 - ii. Alkaline phosphatase $> 1.5 \times ULN$
 - iii. ASAT (SGOT) $> 3 \times ULN$
 - iv. ALAT (SGPT) $> 3 \times ULN$
 - v. GGT $> 3 \times ULN$
- c. RENAL FUNCTION
 - i. UN $> 1.3 \times ULN$
 - ii. Creatinine $> 1.3 \times ULN$
- d. ELECTROLYTES
 - i. Potassium $< 0.9 \times LLN$ or $> 1.1 \times ULN$
 - ii. Sodium $< 0.9 \times LLN$ or $> 1.1 \times ULN$
 - iii. Chloride $< 0.9 \times LLN$ or $> 1.1 \times ULN$
 - iv. Bicarbonate $< 0.9 \times LLN$ or $> 1.1 \times ULN$

- v. Calcium $< 0.9 \times \text{LLN}$ or $> 1.1 \times \text{ULN}$
- vi. Phosphate $< 0.9 \times \text{LLN}$ or $> 1.1 \times \text{ULN}$

Notable abnormalities for subjects with abnormal Baseline results are subject to the primary criteria above and the following secondary criteria:

a. HEMATOLOGY

- i. Hemoglobin $< 0.75 \times \text{Baseline}$ (same as primary criterion)
- ii. Platelets $< 0.75 \times \text{Baseline}$ or $> 1.25 \times \text{Baseline}$
- iii. WBC count $< 0.75 \times \text{Baseline}$ or $> 1.25 \times \text{Baseline}$
- iv. Neutrophils (absolute) $< 0.5 \times \text{Baseline}$ or $> 1.5 \times \text{Baseline}$
- v. Eosinophils (absolute) $> 1.5 \times \text{Baseline}$
- vi. Lymphocytes (absolute) $< 0.5 \times \text{Baseline}$ or $> 1.5 \times \text{Baseline}$

b. LIVER FUNCTION

- i. Total bilirubin $> 1.5 \times \text{Baseline}$
- ii. Alkaline phosphatase $> 1.5 \times \text{Baseline}$
- iii. ASAT (SGOT) $> 1.5 \times \text{Baseline}$
- iv. ALAT (SGPT) $> 1.5 \times \text{Baseline}$
- v. GGT $> 1.5 \times \text{Baseline}$

c. RENAL FUNCTION

- i. UN $> 1.3 \times \text{Baseline}$
- ii. Creatinine $> 1.3 \times \text{Baseline}$

d. ELECTROLYTES

- i. Potassium $< 0.9 \times \text{Baseline}$ or $> 1.1 \times \text{Baseline}$
- ii. Sodium $< 0.9 \times \text{Baseline}$ or $> 1.1 \times \text{Baseline}$
- iii. Chloride $< 0.9 \times \text{Baseline}$ or $> 1.1 \times \text{Baseline}$
- iv. Bicarbonate $< 0.9 \times \text{Baseline}$ or $> 1.1 \times \text{Baseline}$
- v. Calcium $< 0.9 \times \text{Baseline}$ or $> 1.1 \times \text{Baseline}$
- vi. Phosphate $< 0.9 \times \text{Baseline}$ or $> 1.1 \times \text{Baseline}$

4.3.7. ECG

ECG results will be tabulated as “normal” or “abnormal” at each visit and will be presented in a normal/abnormal shift table between Baseline and each scheduled ECG visit, as well as between Baseline and the last ECG taken. Descriptive statistics will be presented for continuous variables (e.g., heart rate and RR, PR, QRS, QT, QTcB, and QTcF intervals) at each visit. A by-patient listing will be provided for ECGs which are deemed abnormal.

4.4. Other Analyses

4.4.1. Subgroup

The following subgroups are defined. Analyses on subgroups are considered as exploratory.

Baseline VA (< 50 vs. ≥ 50 ETDRS letters), Baseline GA (< 4 vs. ≥ 4 disc area), Pattern of FAF at the junctional zone of geographic atrophy (none/focal vs. banded/diffuse) as well as age (< 65 vs. $65\sim 74$ vs. $75\sim 84$ vs. ≥ 85), gender (male vs. female), race (American Indian/Alaska Native vs. Black or African American vs. Asian vs. Native Hawaiian/Pacific Islander vs. White vs. Other), and ethnicity (Hispanic or Latino vs. Not Hispanic or Latino).

4.5. Changes to Protocol-planned Analyses

The following changes are made from protocol planned analyses:

- Time to vision loss analysis based on BCVA was added after primary analysis on Year 1
- GA growth rate without square root transformation
- Piece-wise analysis by every 6-month interval on GA growth rate

5. Supporting Documentation

5.1. [Redacted] *CCI* [Redacted]

[Redacted]

[Redacted]	[Redacted]	[Redacted]
[Redacted]	[Redacted]	[Redacted]
[Redacted]	[Redacted]	[Redacted]
[Redacted]	[Redacted]	[Redacted]
[Redacted]	[Redacted]	[Redacted]
[Redacted]	[Redacted]	[Redacted]
[Redacted]	[Redacted]	[Redacted]
[Redacted]	[Redacted]	[Redacted]
[Redacted]	[Redacted]	[Redacted]
[Redacted]	[Redacted]	[Redacted]
[Redacted]	[Redacted]	[Redacted]
[Redacted]	[Redacted]	[Redacted]
[Redacted]	[Redacted]	[Redacted]
[Redacted]	[Redacted]	[Redacted]
[Redacted]	[Redacted]	[Redacted]

CCI

[REDACTED]	[REDACTED]	[REDACTED]
[REDACTED]	[REDACTED]	[REDACTED]
[REDACTED]	[REDACTED]	[REDACTED]
[REDACTED]	[REDACTED]	[REDACTED]
[REDACTED]	[REDACTED]	[REDACTED]
[REDACTED]	[REDACTED]	[REDACTED]
[REDACTED]	[REDACTED]	[REDACTED]
[REDACTED]	[REDACTED]	[REDACTED]
[REDACTED]	[REDACTED]	[REDACTED]
[REDACTED]	[REDACTED]	[REDACTED]

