A brief SAP addendum (version 1.0) for cumulative Year 2 data of ISEE2008 study was approved on 3 August 2022 before the unmasking of Year 1 data for primary analysis. The addendum prespecified mainly sequential statistical testing procedure on Year 2 (Supporting Document).

The purpose of this SAP (Year 2) is to expand the addendum to provide technical details for the Year 2 and the final analysis of the study.

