1.3. Study Period and Visit Window Definition

Study assessments in Year 2 are summarized below.

Year 2

2. Statistical Hypotheses

The following hypothesis testing will be conducted sequentially.

1. Hypothesis testing in EM vs. Sham for mean GA growth rate are:

$$H_0: \Delta = 0$$

$$\text{versus } H_1: \Delta \neq 0,$$

where $\Delta = \mu_1 - \mu_2$, μ_i is the mean growth rate (slope) of GA over 24 months for treatment EM, or Sham, respectively.

2. Hypothesis testing in ACP 2mg vs Sham for time to vision loss will be conducted using Kaplan-Meier method with a log-rank test
3. Hypothesis testing in EOM vs. Sham for mean GA growth: similarly, as in (1)
4. Hypothesis testing in ACP 2mg vs Sham for mean change in best corrected visual acuity (BCVA in ETDRS letters) from Baseline to Month 24
5. Hypothesis testing in ACP 2mg vs Sham for mean change in low luminance best corrected visual acuity (LL BCVA in ETDRS letters) from Baseline to Month 24

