6. CCI

The hypothesis testing will be evaluated according to a pre-specified hierarchical testing procedure to control overall type-1 error at a 5% two-sided significance level. If the primary analysis testing GA growth rate (ACP 2mg vs Sham) based on Year 1 data is statistically significant, the hypotheses tests will be performed in a sequential way as described above to control familywise type I error rate with 2-sided significance level of 0.05. A test will be performed only if all the preceding tests are statistically significant.

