2.1. Multiplicity Adjustment

There will be no adjustment for the multiplicity as the hypotheses will be tested in a hierarchical procedure on the primary endpoint and the secondary endpoints described above.

3. Analysis Sets

For the purposes of analyses, the following analysis sets (populations) will be used and are defined below.

Participant Analysis Set (population)	Description
Intent-to-treat analysis set (ITT)	All randomized participants who received at least one dose of study drug. Participants will be analyzed in the treatment group assigned at randomization
Safety analysis set (Safety)	All participants who received at least one dose of study drug. Subjects who have ever received an injection of ACP during this trial will be analyzed in the ACP group.
Re-randomized analysis set (Re-Rand)	The subset of ITT population who are re-randomized at Month 12

In the ITT/Safety population, ACP (ARC1905 2mg) and Sham will be used as treatment groups. Subjects who were discontinued from the study in Year 1 will be included. In the Re-randomized population, ARC1905 2mg EM, ARC1905 2mg EOM, and Sham will be used as treatment groups. Subjects who were discontinued from the study in Year 1 will be excluded.

4. Statistical Analyses

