4.2.2.1. Definition of the Estimand

This secondary efficacy objective is to demonstrate that ACP 2 mg can significantly reduce the rate of persistent vision loss compared to Sham up to Month 24.

The following 5 attributes define the secondary Estimand for the secondary endpoint evaluation:

A. Population:

Subjects with geographic atrophy secondary to dry age-related macular degeneration. Analysis will be performed on all randomized patients who received at least one dose of study drug (ITT population).

B. Interventions:

ACP 2mg versus Sham.

C. Endpoint:

Time to persistent vision loss (BCVA ≥ 15 letters loss from Baseline at 2 or more consecutive visits) during the study from Baseline to Month 24.

D. Intercurrent events (ICE's) and strategies:

1. Treatment changes (i.e., interruptions, non-adherence, dose changes, discontinuation): "treatment policy" – i.e., treatment changes will be ignored, and all data collected will contribute to the analysis regardless of whether these follow such ICE's.
2. COVID-19: "treatment policy" – i.e., impact of COVID-19 pandemic will be ignored, and all data collected will contribute to the analysis regardless of whether these follow such ICE's.

E. Population-level summary:

Cumulative rate of persistent vision loss

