5.2. Statistical Analysis Plan Addendum for Cumulative Year 2 Data

Cumulative ISEE2008 year 2 data will be analyzed in a similar way as year 1 data with the following changes.

[figure not shown]

The data will be summarized in 4 groups: Sham, ACP every month (EM), ACP every other month (EOM), ACP overall. ACP overall group will include patients who discontinued from the study in year 1.

If the primary analysis testing GA growth rate (ACP vs Sham) based on year 1 data is statistically significant, the following ranked hypotheses tests will be performed in a sequential way to control familywise type I error rate with 2-sided significance level of 0.05 using similar MMRM specified in year 1 SAP without the stratifications factors. A test will be performed only if all the preceding tests are statistically significant.

1. Mean GA growth rate of ACP EM is lower than Sham based on GA area measured by FAF in 5 time points: baseline, month 6, month 12, month 18 and month 24.
2. Mean GA growth rate of ACP EOM is lower than Sham based on GA area measured by FAF in 5 time points: baseline, month 6, month 12, month 18 and month 24.
3. Mean change in best corrected visual acuity (BCVA in ETDRS letters) from Baseline to Month 24 in ACP is different from Sham based on monthly data from month 1 to month 24.
4. Mean change in low luminance best corrected visual acuity (LL BCVA in ETDRS letters) from Baseline to Month 24 in ACP is different from Sham based on change from baseline data from the following 4 time points: month 6, month 12, month 18 and month 24.

5. [REDACTED] *CCI* [REDACTED]

6. References

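### Year 2 SAP: time to vision loss, added after the Year 1 analysis and counting Year 1 events, is ranked second in a hierarchy called pre-specified, so 5% familywise control is not shown for that claim

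*SAP*

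**What the plan says.** Two testing orders appear in the Year 2 SAP.

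- **Addendum v1.0, reproduced in section 5.2.** The Introduction says it was "approved on 3 August 2022 before the unmasking of Year 1 data for primary analysis". Its order is EM vs Sham, EOM vs Sham, mean BCVA change, mean low-luminance BCVA (LLBCVA) change, then a redacted item. Item 2 reads: "Mean GA growth rate of ACP EOM is lower than Sham based on GA area measured by FAF in 5 time points".
- **SAP v2.0, section 2, dated 22 June 2023.** The order is EM, time to vision loss, EOM, BCVA, LLBCVA, then a redacted item. For rank 2: "Hypothesis testing in ACP 2mg vs Sham for time to vision loss will be conducted using Kaplan-Meier method with a log-rank test". Section 4.2.2.2 confirms that this log-rank p-value feeds the hierarchy.

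On error control, section 2 of v2.0 states: "The hypothesis testing will be evaluated according to a pre-specified hierarchical testing procedure to control overall type-1 error at a 5% two-sided significance level". Section 2.1 adds: "There will be no adjustment for the multiplicity as the hypotheses will be tested in a hierarchical procedure".

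On timing, section 4.5 states: "Time to vision loss analysis based on BCVA was added after primary analysis on Year 1". On the event window, the estimand in section 4.2.2.1 covers persistent loss "during the study from Baseline to Month 24", in the ITT set.

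On the status of v2.0, the Introduction says: "The purpose of this SAP (Year 2) is to expand the addendum to provide technical details". The version history and section 4.5 both mention the added vision-loss analysis. Neither says that it enters the hierarchy above EOM.

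**The concern.** A fixed sequence controls familywise error at the full 5% without further adjustment only if each test and its rank are chosen independently of the data tested. The plan does not show this for vision loss. The endpoint was chosen after the Year 1 analysis, and part of the data it tests is Year 1 data.

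Year 1 acuity data had been collected and were in the scope of that analysis. BCVA is a listed safety outcome in the Year 1 SAP, whose general conventions call for tables by arm. V2.0 also argues from Year 1 results: section 4.2.1.2 justifies dropping the square-root transformation by how the GA slopes turned out.

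If nothing changes, a significant vision-loss result would be reported as confirmatory and pre-specified without support for either label. EOM, which had the second rank in the approved order, could be claimed only if vision loss were also significant. A reader would learn of that change only by comparing section 2 with section 5.2.

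**Working it through.** **1. The plan's own figure.** If the order is fixed without reference to the data, the first true null in the sequence is rejected with probability at most 0.05. A simulation of the approved order with its four legible tests all null gave 0.0505 (1,000,000 runs), which agrees with 5%. The v2.0 order, treated as if chosen without data, with EM effective and vision loss null, gave 0.047. The hierarchy is sound as a procedure. What is in doubt is whether rank 2 was chosen independently of the data.

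**2. What Year 1 knowledge could do.** The documents give no promotion rule and no event counts, so every input here is assumed.

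- Z_final = √f · Z1 + √(1−f) · Z2, where f is the Year 1 share of the vision-loss information.
- Vision loss is promoted to rank 2 if Z1 > c; otherwise the approved order is run.
- EM is taken as rejected; vision loss and EOM are both null; their correlation is 0, 0.3 or 0.6.
- Familywise error = P(Z1 > c and |Z_final| > 1.96) + P(Z1 ≤ c and |Z_EOM| > 1.96).

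| Quantity | c | f = 0.30 | f = 0.45 | f = 0.60 |
|---|---|---|---|---|
| Familywise error, correlation 0 | 1 | 5.8% | 6.1% | 6.4% |
| | 1.645 | 5.6% | 5.9% | 6.2% |
| Familywise error, correlation 0.6 | 1 | 5.5% | 5.7% | 5.8% |
| | 1.645 | 5.4% | 5.6% | 5.8% |
| False significance of vision loss, given promotion | 1 | 10% | 12% | 14% |
| | 1.645 | 17% | 23% | 30% |

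Three checks locate the problem:

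- With f = 0, familywise error is 5.0% at every c and correlation. The whole excess comes from the Year 1 overlap.
- EOM's own error is 4.2–4.8% across the settings in the table. An extra gate cannot raise it.
- Milder selection does less. At f = 0.10 familywise error is 5.1–5.3%. Promotion on any favourable trend (c = 0) leaves the two-sided error at 5.0%, but a promoted test then falsely shows benefit 4.4–5.0% of the time (f = 0.2–0.6) against a nominal 2.5%.

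**3. What the new gate costs EOM.** With 200 per arm (about 400 randomized 1:1), an assumed 24-month Sham rate s and an assumed hazard ratio HR:

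- Events = 200 × [s + 1 − (1−s)^HR]
- Power = Φ(√(events/4) × |ln HR| − 1.96)

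| s | HR 0.5: events, power | HR 0.7: events, power |
|---|---|---|
| 6% | 18.1, 31% | 20.5, 12% |
| 12% | 36.4, 55% | 41.1, 21% |
| 20% | 61.1, 77% | 68.9, 32% |
| 35% | 108.8, 95% | 122.1, 50% |

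Assume next that EM and EOM each have 80% or 90% power. Their contrasts correlate at 1/3 (100:100:200 with a shared Sham arm), and vision loss correlates at 0 or 0.3 with both. The chance of claiming EOM is then:

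| Order | 80% power each | 90% power each |
|---|---|---|
| Approved order | 67% | 82% |
| v2.0, vision-loss power 12% | 8–10% | 10–11% |
| v2.0, vision-loss power 55% | 37–42% | 45–49% |
| v2.0, vision-loss power 95% | 64–65% | 78–79% |

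The smallest loss is 67 − 65 = 2 points and the largest 82 − 10 = 72 points.

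**The case against.** The strongest defence is masking. Protocol 11.7.1 allows details to be fixed before unmasking at Month 12 and again at Month 24. Protocol 11.4 keeps post-Month-12 information masked, and nothing shows that v2.0 missed the Month 24 unmasking. Protocol 11.6.3 keeps the Sponsor masked to treatments until the study ends. This stands for the post-Month-12 part of the endpoint. It does not cover the Year 1 part: Year 1 data were unmasked for the primary analysis, and a plan that argues from Year 1 results cannot rest on Sponsor masking for that year.

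It is also fair that no visible text shows anyone saw BCVA by arm before v2.0, that section 4.2.2 gives a clinical reason for the 15-letter definition, and that other thresholds are planned as sensitivity analyses. These points limit the claim to control that is not demonstrated. They do not establish that endpoint and rank were chosen independently of Year 1 data.

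On disclosure, section 4.5 is headed as changes from the protocol, and the visible protocol contains no Year 2 hierarchy, so the version history is the more natural place for the rank change. The change is strictly one insertion: the other legible tests keep their relative order, and both orders can be read in the document. Even so, no list of changes states the new rank, and demoting EOM is more than technical detail.

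Finally, the promotion rule in the calculation is hypothetical. The 10–30% figure is conditional on promotion and is not the trial's error rate.

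**Conclusion.** The concern holds. Endpoint and rank were set after the Year 1 analysis, the test reuses Year 1 data, and the plan still claims a pre-specified hierarchy at 5% with no other adjustment. Familywise control is not demonstrated for the vision-loss claim; the documents do not show that it is actually lost.

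The size is unknown and may be nil. Under the assumed promotion thresholds (Year 1 z above 1 or 1.645) and Year 1 information shares of 30–60%, familywise error is 5.4–6.4%, with all of the excess in the vision-loss claim. The Year 1 primary test and EM at rank 1 are unaffected. EOM, BCVA and LLBCVA keep their error control and lose only power: for EOM about 2 to 72 points, a range that reflects assumed event rates, hazard ratios and power.

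It should be fixed before the final analysis, because otherwise a claim would carry a confirmatory label that the plan's own section 4.5 does not support.

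**What to change.** 1. Run the confirmatory sequence in the order approved on 3 August 2022: EM, EOM, BCVA, LLBCVA, then the redacted item.
2. Report time to vision loss outside that sequence, with a nominal p-value and confidence interval, labelled as added after the Year 1 analysis.
3. Do not call this endpoint or its rank pre-specified in section 2.
4. Record the rank change against the addendum in the version history and in section 4.5.

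Moving vision loss to the end of the sequence would free EOM from the gate but leave the selection question open for the vision-loss claim itself. A record of who had access to Year 1 BCVA by arm would be useful alongside these changes.

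The cost is SAP wording, with no new data or visits. The downside is that the vision-loss result becomes supportive.
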